Participants assigned to receive WASABI will complete at least 3 EMA sessions per week, 1 hour of digitally delivered Cognitive Behavioral Group Therapy (dCBGT) per week, and weekly cognitive biases assessments and self-reports for 12 weeks. During the intervention, these participants will also have daily access to 1:1 and group chat Instant Messaging (IM) and may have weekly electronic check-ins with Site Study personnel (as needed). Participants in the control condition will be asked to attend 1 hour of digitally delivered Cognitive Behavioral Group Therapy (dCBGT) per week for 12 weeks and may have weekly electronic check-ins with Site Study personnel (as needed).

For each arm, as soon as 3-6 participants have completed the baseline assessments and randomization, a cohort will be assembled. The Study Coordinator will meet with the participants to orient them to the study platforms and the WASABI Clinician will meet with each participant individually for a brief introduction and orientation prior to the 12-week intervention and will review of the *Procedures and Guidelines to Group Therapy*. The WASABI Coordinator and/or Clinician will create a virtual support group open only to cohort participants. The WASABI Clinician will explain her role, make group introductions, and will invite participants to attend weekly 1-hour group sessions (dCBGT+ WASABI or dCBGT only, depending on the treatment arm). For the treatment group (dCBGT + WASABI), between group sessions, the WASABI Clinician will spend approximately 30 min/day keeping the chat active during work hours, checking it approximately 3 times a day and may respond to messages participants leave, as appropriate. The WASABI Coordinator will be included in the support group chat and may monitor the chat content, and may be active in the chat in the absence of the WASABI Clinician.

Participants will be re-evaluated again at the expected time of completion, immediately following the 12-week intervention, to evaluate changes in performance. Finally, participants will be asked to fill out an online exit survey to rate enjoyment, usability, perceived benefits, and ease of fit into schedule.

The protocol will be conducted in accordance with the protocol submitted to and approved by the reviewing Institutional Review Board and approval will be obtained prior to implementation.

Study Population

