Participants expressing interest in the study that do not meet certain eligibility criteria, e.g. have experienced a change in medication or have been hospitalized within the last 4 weeks, have an upcoming medical procedure, surgery or treatment that would interrupt their participation, have experienced suicidal ideation or behavior within two months or those with known future end dates to psychotherapy treatment, will be placed on hold and re-screened for appropriate eligibility criteria.

Study Procedures/Research

Study Procedures: Participants at the recruitment Site will flow through the study in the following manner:

1. *Informed Consent Discussion:* Site Study personnel will discuss study goals, activities, and requirements with the parent/legal guardian and/or potential participant; complete the informed consent discussion, and if/when appropriate the potential participant will complete assent/consent to join study.
Duration: ~30-60 minutes remotely or in-person at the Study Site.
2. *Initial Screening Visit (V0):* Following assent/consent, Site Study personnel will perform diagnostic assessments and interviews and assess inclusion/exclusion to determine if the participant is eligible for enrollment.
Duration: ~2-3 hours remotely or in-person at the Study Site. The *Informed Consent Discussion* and the *Initial Screening Visit (V0)* may occur independently or may be combined in a single session.
3. *Baseline Assessment (V1):* Following enrollment, the participant will perform all social/cognitive baseline characterization assessments and questionnaires prior to the intervention period. Duration: ~2 hours remotely or in-person at the Study Site.
4. *Randomization:* Participants will be randomized into one of two treatment groups.
5. *Mobile device Set-Up and Proctored Application Use (V2):* The participant will be oriented to the intervention activities and program application(s). Participants assigned to both WASABI and the active control arm will complete a series of mobile assessments during this visit (embedded baseline assessments via BrainHQ) .

Participants with a compatible personal device that are willing to download the necessary application(s) for program use will have their device set-up at this visit. Participants assigned to WASABI will be guided to schedule reminders for

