We hypothesize that the innovative features of WASABI will improve the quality of treatment delivery and facilitate the generalization of trained skills into real-world settings. The measures collected to determine the efficacy of the program for this trial are clinical ratings of anxiety and social anxiety symptoms (LSAS-CA), self-report inventories of social anxiety symptoms (SPAI), broad measures of anxiety (MASC-2), self-report inventories of social skills (SSQ), and self-report inventories of social functioning (ASSES). To test this hypothesis, we will use a linear mixed model approach. We will first compare treatment and active control groups in the ITT population to determine if any differences in baseline demographic, characterization, outcomes variables, or total program use time remain after the randomization process. Any such factors that show trend level significant differences ($p < 0.1$) will be noted and used as covariates in the linear mixed model analysis. The criterion for statistical significance is $p < 0.05$. Results with $p < 0.1$ will be described as trends.

Performance on the attention bias and interpretation bias assessments will be modeled longitudinally to examine if these measures can serve as potential moderators and mediators. To test if the attenuation of attention and interpretation biases mediates improvements in outcome measures, we will use repeated-measures linear mixed modeling to test in the active group the effects of WASABI on LSAS-CA, SPAI, SSQ and ASSES, and then model outcomes as a function of performance improvements on the attention bias and interpretation bias assessments.

Because we are interested in examining the ecological validity of WASABI, we will not restrict the analyses only to participants who adhered to all intervention requirements. Within-group effect sizes (Cohen's d) will be computed using the mean change scores (post-intervention minus baseline) and the change score SDs.

These measures will be analyzed to power the pivotal study proposed for Phase II. For the FDA, we will collect data documenting that WASABI meets its design requirements when used in the field by clinicians and patients, and that clinicians deem its risk/benefit ratio as acceptable and view it as adequate/appropriate for the target population.

Data Management

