Statistical Analysis Plan

WASABI: Wiring Adolescents with Social Anxiety Via Behavioral Interventions

Protocol Number: PSC-1016-19

NCT03990870

Document Date: July 8, 2019

(1) ANALYSIS POPULATIONS

There are three *a priori* defined analysis populations, including a primary analysis population (i), a secondary analysis population designed to compare effect sizes in populations with no missing data (ii) and a population who completed all training visits (iii)

- i. *Intent to Treat (ITT) population:* This is the *a priori* primary analysis population, defined as including all randomized participants who attended at least one group video call.
- ii. *Intent to Treat (ITT) Fully-Evaluable (FE) population:* This is a secondary analysis population, defined as including all members of the ITT population that complete a post-intervention visit. Note that a participant may complete a specific visit but have missing data for a test in which case the participant is in the overall FE population but does not contribute data to the FE population for that visit, e.g., the number of evaluable cases for a specific test on a specific visit may be smaller than the FE population for that visit because of missing data.
- iii. *Intent to Treat (ITT) Completers (C) population:* This is a secondary analysis population, defined as including all members of the ITT-FE population who complete all intervention sessions. Note that the C populations are strict subsets of the FE populations; a person who completes the target number of videocalls but does not complete the evaluation visit is not a member of the C population.

(2) STATISTICAL PLAN

Feasibility

The Phase I data analysis plan *a priori* defines a primary intent-to-treat (ITT) population, a set of secondary evaluation populations, a set of primary outcome measures, a set of secondary outcome measures, a set of potential mediators/moderators, a single primary evaluation time point, a criterion for statistical significance, and a statistical analysis methodology for secondary outcomes.

- The primary ITT population is defined as all participants who attend one dCBGT video call. Note that this includes all randomized participants except those who drop/withdraw post-randomization and pre-training.

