For feasibility, we relied on descriptive statistics. For preliminary efficacy, in smaller sample sizes like ours, there is a greater likelihood that there will be larger differences at baseline between groups simply due to sampling error. Groups were compared on all baseline measures using Mann-Whitney U tests (for ordinal and continuous variables) or Pearson chi-square/Fisher's exact test (for categorical variables). To test whether groups differed in change over time, data were analyzed via linear mixed-effects models. Mixed-effects models are ideal for the analysis of longitudinal data, due to the fact that it tolerates missing observations—assuming that it is missing at random (MAR). First, simple growth models (change from baseline to post) were conducted to examine change over time (for all participants). Because complete case analyses have been shown to provide biased estimates in the presence of missing data (Enders, 2010), data were then modeled using the intent-to-treat (ITT) framework, in which all randomized subjects are included in the analysis, and missing data were handled via Full Information Maximum Likelihood (FIML). This method for handling missing data is considered a gold standard approach, as it gives relatively unbiased estimates (Enders, 2010), and is the standard for the analysis of randomized trials. For all models, fixed effects of time, group, and group x time interaction were included; a random intercept of subject was used. Kenward-Roger degrees of freedom were used due to the small sample size; statistical significance was evaluated at a two-sided alpha of $p = 0.05$; however, null hypothesis testing was de-emphasized given the small sample size of the control group ($n = 8$). We emphasize the effect size (Cohen's d) instead. Although various estimates of effect size exist for LMM, we chose a simplified version, defined as:

$$\frac{(\Delta_{(dCBT+WASABI)} - \Delta_{(dCBT)})}{\sigma_{pre}}$$

Where Δ refers to slope (i.e., change from baseline to post-intervention) and σ_{pre} refers to the pooled baseline standard deviation. Thus, values of d refer to change in standard deviation units from baseline.

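### The SAP uses the ITT label for two different sets, randomized participants who attended at least one call and all randomized, which leaves the feasibility denominators unsettled

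*SAP*

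**What the plan says.** SAP section (1), Analysis Populations, names a primary ITT population "defined as including all randomized participants who attended at least one group video call". Section (2), under Feasibility, repeats the attendance condition: "The primary ITT population is defined as all participants who attend one dCBGT video call". It then states the consequence openly: "this includes all randomized participants except those who drop/withdraw post-randomization and pre-training".

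Two other places in section (2) point to a different set. The list of primary outcomes opens by saying that they are analysed in those randomized to WASABI plus dCBGT, with no attendance condition. The closing paragraph on the mixed models describes an ITT framework "in which all randomized subjects are included in the analysis", with missing data handled by full-information maximum likelihood.

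The protocol does not resolve this. Its Data Analysis section says "We will first compare treatment and active control groups in the ITT population" but never defines that population. Its General Study Design section shows why there is a gap in which people can be lost: for each arm, "as soon as 3-6 participants have completed the baseline assessments and randomization, a cohort will be assembled".

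**The concern.** Two analysts could each follow the SAP faithfully and use different primary sets. The section (1) set is a modified ITT set carrying the ITT label, while the mixed-model paragraph claims the properties of a full ITT analysis.

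The difference matters most for the main purpose of this Phase I trial, which is to find out whether WASABI is feasible, acceptable and usable. Someone who is randomized and never joins a call is a feasibility failure. Under the section (1) definition that person leaves the denominators of the completion and engagement rates.

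The gap between randomization and the first call is part of the design. It holds the device set-up visit, the individual orientation and the wait for a cohort to form within the participant's own arm. Loss in that gap could therefore differ between arms, although the documents do not show that it does.

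The arms are small: 12 completers per arm are planned, and the SAP gives a control group of 8. One or two exclusions could shift the baseline comparison, the covariates that the protocol selects from it at p < 0.1, and the pooled baseline SD that divides Cohen's d.

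**Working it through.** **1. The definitions side by side.** Take a participant who is randomized and withdraws before the first call.

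- SAP section (1) and the first bullet under Feasibility: excluded.
- SAP section (2), introduction to the primary outcomes: included if randomized to WASABI plus dCBGT.
- SAP section (2), mixed-model paragraph: included.

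A participant who withdraws after one call is in the set under all three. The conflict concerns non-starters only.

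**2. How many non-starters?** The documents do not say. The protocol plans about 32 consented to obtain 24 completers, a margin of 1 − 24/32 = 25%. That margin starts at consent, before eligibility is determined, so it also covers screen failures and cannot be read as loss after randomization. The number of non-starters, k, must be assumed.

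**3. The completion target.** The SAP states at least 79%, glossed as at least 8 of 12. These disagree: 8/12 = 66.7%, while 0.79 × 12 = 9.48, so 79% needs 10 of 12.

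**4. Sensitivity of the completion rate.** Let N be the number randomized to the WASABI arm and c the number of completers. The rate is c/N over all randomized and c/(N − k) over those who attended a call. Assume N = 12 and c = 8, the SAP's own pair:

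| k (assumed) | all randomized | attended at least one call |
|---|---|---|
| 0 | 8/12 = 66.7% | 8/12 = 66.7% |
| 1 | 8/12 = 66.7% | 8/11 = 72.7% |
| 2 | 8/12 = 66.7% | 8/10 = 80.0% |
| 3 | 8/12 = 66.7% | 8/9 = 88.9% |

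From k = 2 the same 8 completers pass 79% on the one-call set and miss it on the full set. The crossing does not always occur. With c = 10 and N = 12, the rate is 10/12 = 83.3% over all randomized and higher on the one-call set, so both pass. Read as 8 of 12, the target is met by 8 completers on either set.

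**5. Engagement.** The target is attendance at 80% of sessions. With k = 2 of 12, if the 10 starters average exactly 80%, the mean over all randomized is 0.80 × 10/12 = 66.7%.

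**6. Assessment adherence.** This outcome has its own, stricter filter. The protocol's Data Analysis section counts it among those who reached two group calls and five EMA completions, and the SAP directs assessment efforts to the same group. Changing the ITT definition alone would not alter it.

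**7. Efficacy.** Baseline comes before randomization in the protocol's Study Procedures: "the participant will perform all social/cognitive baseline characterization assessments and questionnaires prior to the intervention period", with randomization as the next step. A non-starter therefore has baseline data and can enter the mixed model. The end-of-study visit, however, is offered to participants who have met a minimum number of sessions (protocol, program-use flexibility and Withdrawal from the Protocol). A non-starter would ordinarily contribute baseline only. Such a record informs the baseline mean and variance but adds little on change.

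**The case against.** The strongest reply has four parts.

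- **The exclusion is disclosed and narrow.** This is correct. A reader might infer that all dropouts after randomization leave the primary set. The SAP does not say that: only those lost before the first call do. Disclosure does not, however, reconcile section (1) with the mixed-model paragraph.
- **The feasibility list already refers to randomized participants.** This also stands. A reader might infer that the completion and engagement rates are certain to be overstated. The documents do not support that, because the primary-outcome list offers a randomized-arm denominator. The one-call bullet sits under the same Feasibility heading, so the denominator is ambiguous.
- **The primary outcomes are descriptive and single-arm.** An argument about breaking the randomized comparison therefore does not reach them. It applies only to the secondary between-arm contrast, for which the protocol admits insufficient power and the SAP de-emphasizes testing.
- **Restoring non-starters does little for efficacy.** A reader might infer that the exclusion biases the treatment contrast by some definite amount and that adding non-starters back would remove it. The documents supply neither a non-starter rate nor their outcomes, so no such figure can be given. If their unobserved outcomes would differ in ways that the observed data do not predict, missing at random fails and baseline-only records do not correct it.

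What remains is the conflict of definitions and its effect on the primary feasibility rates if section (1) is followed.

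**Conclusion.** The concern holds as a conflict of definitions with a practical consequence for feasibility. That the SAP gives incompatible statements of its primary population is certain from the text.

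The size of the consequence depends on an unknown number of non-starters. Under the assumption of 12 randomized, 8 completers and 2 non-starters, completion is 67% or 80% according to the denominator, on either side of 79%. With no non-starters there is no difference. The comparison with the target is itself clouded, because 79% and 8 of 12 are not the same threshold.

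For efficacy, one definition would make the analysis set match the SAP's own mixed-model paragraph and preserve the randomized baseline comparison. It should not be presented as removing bias from non-starters' missing outcomes. The change is worth making because the feasibility rates are primary and the results are meant to inform a pivotal trial.

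**What to change.** Amend the SAP so that one definition governs:

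1. Define ITT as all randomized participants, analysed in the arm to which they were randomized. Use it for the feasibility denominators (the WASABI arm) and for the mixed models.
2. Rename the set requiring at least one call modified ITT, and keep it as a sensitivity set. Describe the evaluable and completer sets consistently with this.
3. Report by arm the number randomized who never attended a call.
4. Report assessment adherence over all randomized as well as over those who met the two-call, five-EMA minimum.
5. State the completion target once, as a percentage or as a count, with its denominator.

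The cost is SAP wording and a few extra table rows. No new data collection is needed. The downside is that feasibility rates may come out slightly less favourable.

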Once three participants are deemed eligible and enrolled in the pilot trial, they will be scheduled for three focus group sessions that could occur in-person or remotely, to be completed over the course of approximately 2-weeks. Each session will last approximately 1 hour and will be facilitated by the study clinician(s). After feedback from the focus group sessions is implemented into the app and dashboard design, the three adolescents will be granted access to the WASABI app and engage in a 2-week trial period, during which the predictive ability of the algorithm will be validated by the WASABI clinician, who will verify via 1:1 remote videocalls the actual presence of clinically-significant social anxiety whenever the WASABI clinician receives an alert. Additionally, this trial period will ensure that WASABI EMA data are timely evaluated by the clinician on the dashboard and meaningfully orient the delivery of individualized IM and weekly dCBGT content. At the end of the 2-week trial period of WASABI, participants will be asked to rate their enjoyment, ease of use, product quality, and perceived usefulness in a 1:1 user interview. Finally, we will submit these data from the trial period to our consultant to confirm that WASABI is suitable for the feasibility trial.

General Study Design

We will employ a standard prospective, parallel arm, double-blind, randomized, controlled clinical trial to assess the safety and efficacy of WASABI in adolescents with Social Anxiety (SA), and evaluate its potential in augmenting the efficacy of dCBGT in improving social

anxiety, social skills and social functioning. We will randomize adolescents with SA (ages 14-18) to receive either 12 weeks of dCBGT+WASABI or dCBGT only.

Approximately 32 participants will be consented to ensure the successful completion of 24 participants (12 participants per treatment arm). A diagnostic interview will be performed to determine eligibility. Following inclusion and enrollment, participants will complete a set of assessments prior to the intervention to establish their baseline performance. Participants will then be randomized to dCBGT+WASABI or dCBGT only and spend up to 12 weeks engaged in their assigned intervention.

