- As the main goal of this Phase I trial is to evaluate the feasibility, acceptability and usability of the WASABI app. To this purpose, we will conduct an analysis of the following primary outcome measures in participants randomized to the WASABI+dCBGT arm:
 1. Assessment adherence (percentage of assessment sessions attended). Efforts will be made to assess all participants who have completed the minimum required intervention activities (attended at least 2 group calls, completed EMAs at least five times). *Based on our previous studies (CLIMB and MOODIFY) and pilot, we expect successful data collection of baseline and post-intervention outcome measures for ≥90% of participants.*
 2. Engagement with the digitally delivered Cognitive Behavioral Group Therapy (dCBGT) and with group Instant Messaging (IM): number of group sessions attended, number of messages sent per week on the group chat. *Based on our previous studies (CLIMB), we hypothesize that participants randomized to WASABI+ dCBGT will participate in 80% of the dCBGT sessions, and send at least 8 messages/week in the group chat.*
 3. EMA completion rate. *Based on our previous studies and pilot, we hypothesized that participants randomized to WASABI+ dCBGT would respond to 70% of the EMA prompts.*
 4. SPAI-B completion rate. *Based on our previous studies and pilot, we hypothesized that participants randomized to WASABI+ dCBGT would complete the weekly SPAI-B questionnaire 70% of the time.*

5. Overall program completion rate. *Based on findings from our previous findings (CLIMB) and from the pilot in anxious youth, we hypothesized full program completion in $\geq 79\%$ (≥ 8 of 12) study participants in the treatment arm.*

6. Usability ratings were obtained from all study participants post-intervention via a 7-point Likert-scale exit survey. This is a brief and embedded post-study questionnaire on program satisfaction, clarity, enjoyment, perceived benefits, and ease of fit into schedule. Participants rate each sentence on the following 7-point Likert scale: 1 = Completely Agree; 2 = Mostly Agree; 3 = Somewhat Agree; 4 = Undecided; 5 = Somewhat Disagree; 6 = Mostly Disagree; 7 = Completely Disagree. Clinical trials run by Posit Science software using this survey have shown high internal consistency with a Chronbach's alpha of .917. *Based on our previous findings, we hypothesize exit survey ratings of at least $\geq 4.5 \pm 1.5$ on the 7-point Likert scale items.*

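### The program-completion target is given as at least 79% and as at least 8 of 12, but 8 of 12 is 66.7% and 79% of 12 needs 10 completers

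*SAP*

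**What the plan says.** Section (2) of the SAP, under Feasibility, lists seven primary outcomes and says they will be analysed as "primary outcome measures in participants randomized to the WASABI+dCBGT arm". The fifth is the overall program completion rate. Citing an earlier study and the pilot, the SAP states: "we hypothesized full program completion in" at least 79%, with at least "8 of 12) study participants in the treatment arm" as the bracketed equivalent.

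The protocol names the overall program completion rate as a primary outcome (Intervention Embedded Assessments) and again under Data Analysis, but sets no numeric target for it. The figure of 12 per arm matches the protocol's General Study Design: "Approximately 32 participants will be consented to ensure the successful completion of 24 participants (12 participants per treatment arm").

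On the method of analysis the SAP says: "For feasibility, we relied on descriptive statistics".

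**The concern.** A percentage and a count offered as the same threshold should agree at the stated denominator, and these do not. The main goal of the trial is feasibility, and the protocol's Sample Size Justification accepts that 24 evaluated participants are too few to detect an augmentation effect. The primary conclusion therefore rests on benchmarks of this kind. Because the analysis is descriptive, the observed count is read straight against the stated target. A result between the two forms could be reported as a success or as a shortfall, with the SAP cited for either.

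**Working it through.** **Inputs.** Percentage form: at least 79%. Count form: at least 8 of 12, in units of study participants. Both come from SAP section (2), primary outcome 5. Planned arm size: 12 completing participants (protocol, General Study Design).

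**Attempt to reproduce the stated equivalence.**

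- Count to percentage: 8/12 = 66.7%, which is 79 − 66.7 = 12.3 points below the stated percentage.
- Percentage to count: 0.79 × 12 = 9.48, so the smallest whole number that satisfies it is 10.

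The equivalence is not reproduced. The counts around the threshold are:

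| Completers of 12 | Share | At least 8 of 12? | At least 79%? |
|---|---|---|---|
| 7 | 58.3% | no | no |
| 8 | 66.7% | yes | no |
| 9 | 75.0% | yes | no |
| 10 | 83.3% | yes | yes |

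The two forms disagree at 8 and 9 and nowhere else.

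**Readings that might rescue it.**

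- Rounding or truncating 9.48 gives 9, not 8, and 9/12 is still below 79%.
- The unit is participants, so 8 of 12 cannot mean weekly sessions.
- A minimum count of 8 fits 79% only for an arm of 9 or 10 (0.79 × 9 = 7.11 and 0.79 × 10 = 7.9, both rounding up to 8). The SAP says 12.
- Planned retention does not give the figure: 24/32 = 12/16 = 75%.

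**How often the ambiguity would matter.** Let X be the number of completers, binomial with n = 12 and true completion rate p, assuming independent participants. Then P(X = 8 or 9) = P(X ≥ 8) − P(X ≥ 10).

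- p = 0.79 (the SAP's own figure): 0.913 − 0.523 = 0.390
- p = 0.70 (assumed): 0.471
- p = 0.60 (assumed): 0.355

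At a true rate of 79%, then, the chance of meeting the target is about 91% by the count and 52% by the percentage.

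**If the arm is not exactly 12.** The protocol's 12 per arm is the number expected to finish, out of about 32 consented, while the SAP analyses those randomized. Randomizing all 32 in a 1:1 ratio would put 16 in each arm. This is an upper-end assumption, since eligibility is determined after consent.

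| n | Needed for 79% | Needed for the 8/12 share | Counts in the gap | P(gap) at assumed p = 0.70 |
|---|---|---|---|---|
| 12 | 10 | 8 | 8, 9 | 0.471 |
| 13 | 11 | 9 | 9, 10 | 0.452 |
| 14 | 12 | 10 | 10, 11 | 0.423 |
| 15 | 12 | 10 | 10, 11 | 0.425 |
| 16 | 13 | 11 | 11, 12 | 0.414 |

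Two counts stay in dispute at every size. If 8 were carried over as a fixed number, it would be 8/16 = 50% of an arm of 16.

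**The case against.** The strongest reply is that little depends on this figure. The SAP words it as a hypothesis, attaches no decision rule, and analyses feasibility descriptively. If the count and denominator are reported, readers can judge for themselves. That is a fair limit on the consequences, but it does not reconcile the two forms, and a primary outcome's stated expectation should have one meaning.

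The illustrative probabilities can also be challenged. Rates of 60% and 70% are not in the documents, therapy is delivered in cohorts of 3 to 6 so completion may cluster, and 16 per arm ignores screen failures. These points stand, and the probabilities should be read as rough. The contradiction at n = 12 needs none of them.

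Two further points stand and bear on the correction. SAP section (1) defines the primary ITT population as randomized participants who attended at least one group video call, which is narrower than everyone randomized to the arm. And outcome 5 does not define full completion. The nearest definition, the Completers population, requires every intervention session plus the post-intervention visit, whereas the protocol expects some participants to miss sessions.

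**Conclusion.** The target is wrong as written. At the SAP's own denominator of 12 its two forms differ by 12.3 percentage points, or two participants, and contradict each other at 8 and 9 completers. This follows from arithmetic alone. The chance of landing on those counts, 0.39 at a true rate of 79%, additionally assumes 12 independent participants. The documents do not show which form was intended, because the cited earlier study and pilot are offered in support of both.

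The effect is confined to how one primary feasibility outcome is reported; no test or sample size depends on it. It should be fixed, and confidence in the finding is high.

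**What to change.** Replace the sentence with one threshold whose percentage and count agree, and name its source: either at least 79% (at least 10 of 12) or at least 67% (at least 8 of 12). The sponsor must say which was meant.

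State the denominator as all participants randomized to WASABI+dCBGT, as the Feasibility section already has it, and note how that differs from the ITT definition in section (1). If the arm is not exactly 12, derive the count as the chosen percentage of the actual number, rounded up. Say in the same place what counts as full completion.

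Parts of SAP section (2) are in the past tense and give an achieved control-group size: "null hypothesis testing was de-emphasized given the small sample size of the control group" (n = 8). Results may therefore already be known, although the treatment-arm size is not given. If they are, keep the existing sentence visible, label the correction post hoc, and report the observed count against both forms so that the threshold is not chosen after the fact.

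The cost is one SAP line, plus a disclosure sentence if results are known. Either the bar becomes stricter or the stated percentage becomes less favourable. Data collection and analysis do not change.
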